### **8.2.2 Analysis Populations**

#### **8.2.2.1 Efficacy Analysis Populations**

Subjects who either experience documented progressive disease during the first 12 weeks of treatment or complete the first 12 weeks of treatment and undergo re-staging are considered evaluable for objective response evaluation. Subjects who are withdrawn from study (due to toxicity or other reasons) in the first 12 weeks of treatment and who do not undergo re-staging will be considered unevaluable for objective response evaluation but will be included in the safety analyses. The All Patients as Treated population will be used for estimation of PFS and OS.

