	3, 4	Yes	Toxicity improves to Grade 0-1 or baseline	Reduce itacitinib by 1 dose level (100 mg daily)  If second dose reduction is necessary subject will be discontinued from itacitinib treatment.	Toxicity does not resolve within 2 weeks of last dose.  If second dose reduction is necessary subject will be discontinued from itacitinib treatment.
Hepatic Toxicity	Bilirubin $\geq$ 2 x ULN AND Grade 3 AST/ALT ( $\geq$ 3 x ULN)	Yes	N/A	N/A	Discontinue itacitinib

\* N/A = Not applicable

1- Missed doses will not be made up. The subject may receive up to 42 days of itacitinib therapy.

2- If a subject discontinues itacitinib therapy, they may continue on pembrolizumab treatment and may remain on study.

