## **5.8 Subject Replacement Strategy**

Subjects who either experience documented progressive disease during the first 12 weeks of treatment or complete the first 12 weeks of treatment and undergo re-staging are considered evaluable and will not be replaced. Subjects who complete study treatments but are unable to complete planned biopsies will also be considered evaluable for response and adverse events. All other subjects will be considered non-evaluable and will be replaced.

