### **7.1.6 Other Procedures**

#### **7.1.6.1 Withdrawal/Discontinuation**

When a subject prematurely discontinues from study treatment, all applicable activities scheduled for the End of Treatment Safety Follow-up Visit should be performed at the time of discontinuation. Any adverse events which are present at the time of discontinuation/withdrawal should be followed in accordance with the safety requirements outlined in **Section 10**. Subsequent to the End of Treatment Safety Follow-up Visits, subjects will be asked to return for an End of Study Visit as per the Trial Flow Chart in **Section 6.0**.

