##### **Progression Free Survival (PFS)**

CONFIDENTIAL

This material is the property of the University of Pennsylvania. Do not disclose or use except as authorized in writing by the study sponsor.

Progression-free survival (PFS) is defined as days from initiation of study therapy to first documented disease progression, death due to any cause or last subject contact which documents progression-free status. Those patients who are currently on-study and progression-free at 16 weeks, will no longer be followed and will be censored for PFS at week 16.

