#### **8.2.2.2 Safety Analysis Populations**

The All Patients as Treated (APaT) population will be used for the analysis of safety data in this study. The APaT population consists of all enrolled subjects who received at least one dose of study treatment with either itacitinib or pembrolizumab. At least one laboratory or vital sign measurement obtained subsequent to at least one dose of trial treatment is required for inclusion in the analysis of each specific parameter. To assess change from baseline, a baseline measurement is also required.

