### **8.2.3 Statistical Methods**

#### Primary Objectives

1. Based on evaluable subjects, the objective response rate and 95% confidence interval will be calculated.
2. Toxicities will be graded, categorized and tabled. Toxicity tables will be separately constructed for cycles with pembrolizumab alone (cycles 1-2 and cycle  $\geq 5$ ) or pembrolizumab and itacitinib (cycles 3-4).

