### **8.3 Sample Size**

The required sample size ranges from 11 to 48 evaluable subjects. In the event that 5% of subjects are not evaluable for objective response evaluation, the maximum sample size is 50 subjects.

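### The primary response rate drops and replaces treated subjects lost before re-staging, and no all-treated response rate is planned beside it

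*Combined protocol and SAP*

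**What the plan says.** Section 8.2.3 sets the primary analysis: "Based on evaluable subjects, the objective response rate and 95% confidence interval will be calculated". The stage sizes of 11, 19 and 18, and the bounds attached to them, are likewise counted in evaluable subjects (sections 2.1, 5.9 and 8.1).

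A subject is evaluable if progression is documented in the first 12 weeks, or if 12 weeks of treatment are completed and re-staging is done. Section 8.2.2.1 says that those withdrawn earlier, for toxicity or any other reason, and not re-staged "will be considered unevaluable for objective response evaluation but will be included in the safety analyses". Section 2.1 says they are replaced, and section 5.8 closes with a catch-all: "All other subjects will be considered non-evaluable and will be replaced".

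An all-treated population already exists in section 8.2.2.2: "The APaT population consists of all enrolled subjects who received at least one dose of study treatment with either itacitinib or pembrolizumab". It is assigned to safety, PFS and OS, but not to ORR. On expected losses, section 8.3 says: "In the event that 5% of subjects are not evaluable for objective response evaluation, the maximum sample size is 50 subjects".

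**The concern.** Whether a subject enters the primary denominator depends on what happens after treatment starts, including toxicity of the regimen under test. Someone who leaves for toxicity without a scan, or who dies without documented progression, is removed and another subject takes the place. The same death is an event for PFS, which section 8.2.1 measures to "first documented disease progression, death due to any cause or last subject contact which documents progression-free status" in all treated patients. One outcome is thus a failure in one efficacy analysis and absent from another.

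The visit schedule does little to prevent such losses. For a subject who stops treatment early, section 7.1.6.1 asks that "all applicable activities scheduled for the End of Treatment Safety Follow-up Visit should be performed at the time of discontinuation", and the flow chart marks no tumor imaging in that column.

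If those lost are mainly non-responders, the observed ORR is too high, and more so the worse the regimen is tolerated. The result is set against historical pembrolizumab controls (section 3.1), so the denominator matters. The plan does not call for the all-treated figure or the reasons for loss that would show how far this went.

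**Working it through.** **Inputs from the plan.** Stages of 11, 19 and 18 evaluable subjects; stop at 2 or fewer of 11, 12 or fewer of 30, 20 or fewer of 48; null 35%, alternative 55% (section 8.1). Loss 5%, maximum 50 enrolled (section 8.3).

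**Assumptions added here.** The 35% null is an all-treated rate (the documents do not give the benchmark's denominator); a 10% loss as a second scenario; three response rates among dropped subjects: 35%, half of that, and zero.

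**Step 1: reproduce the plan's figures.** Exact three-stage binomial recursion.

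- At 35%: P(stop at stage 1) = 0.2001 and P(stop at stage 2) = 0.5855, together 0.7857 (stated 0.786). P(recommend) = 0.0997 (stated 0.100).
- At 55%: P(recommend) = 0.9057 (stated 0.906).

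All three stated figures are right for evaluable subjects.

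**Step 2: link the two rates.** Let d be the share of treated subjects dropped and q their response rate. If the all-treated rate is 0.35, the evaluable rate is

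p = (0.35 − d·q) / (1 − d).

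For example, d = 0.05 and q = 0 give 0.35/0.95 = 0.368; d = 0.05 and q = 0.175 give 0.34125/0.95 = 0.359.

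**Step 3: run the same design at p.**

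| Share dropped (d) | Their response rate (q) | Evaluable ORR (p) | P(recommend) |
|---|---|---|---|
| 5% (plan) | 35% | 35.0% | 0.0997 |
| 5% (plan) | 17.5% | 35.9% | 0.1245 |
| 5% (plan) | 0% | 36.8% | 0.153 |
| 4% (2 of 50) | 0% | 36.5% | 0.141 |
| 10% (assumed) | 35% | 35.0% | 0.0997 |
| 10% (assumed) | 17.5% | 36.9% | 0.156 |
| 10% (assumed) | 0% | 38.9% | 0.229 |

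**Step 4: effect on a just-passing result (exact 95% CI).** 21/48 = 43.8% (29.5–58.8%). If 50 were treated and the two dropped did not respond, 21/50 = 42.0% (28.2–56.8%), a shift of 43.75 − 42.0 = 1.75 points.

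**Step 5: why not simply change the primary denominator.** Suppose losses counted as failures under the current bounds and 55% is an evaluable-subject rate. Power at 5% loss is the design's value at 0.55 × 0.95 = 0.5225, which is 0.836. At 10% loss it is the value at 0.55 × 0.90 = 0.495, which is 0.739.

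**The case against.** The plan is open about its denominator. It counts evaluable subjects throughout and its error rates are correct for them. If the 35% null is itself an evaluable-subject rate, as the design text is worded, the error stays at 0.0997. The larger figures need both an all-treated null and dropped subjects who respond less often than the rest. All of this stands, and it is why the figures are given as a range that includes no bias.

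The excluded group is also narrower than it may seem. Documented progression stays in as non-response, and section 5.4.2 treats permitted radiation as progression for the primary endpoint. Stopping itacitinib alone need not remove anyone: "If a subject discontinues itacitinib therapy, they may continue on pembrolizumab treatment and may remain on study". A subject who stops treatment is not necessarily withdrawn from study and may still be scanned. An early responder who leaves would be dropped too, which works the other way. These points limit the bias; they do not remove it for toxicity withdrawals, other withdrawals and deaths without documented progression. That deaths fall in this group is an inference from the section 5.8 catch-all, since no section names the case.

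A reader could divide responders by the number treated. That depends on what is reported, is not prespecified, and leaves the reasons for loss unknown.

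Finally, subjects lost in Cycles 1–2 never received itacitinib, so an all-treated ORR charges the combination with some failures that precede it. That is a fair limitation. It argues for showing the timing of each loss and for keeping the all-treated ORR as a sensitivity analysis.

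**Conclusion.** The concern holds. The exclude-and-replace rule can bias the decision-making ORR upward, and the plan has no all-treated ORR against which to judge it. The stated 0.100 and 0.906 are not miscalculated; they apply to evaluable subjects and need not hold for treated subjects.

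At the planned 5% loss the shift in the estimate is small (under 2 points for a just-passing result with two losses), but the chance of a false recommendation could rise by up to about half, from 0.0997 to 0.153. That upper figure rests on the all-treated reading of the null and on no dropped subject responding. If loss is unrelated to response, there is no inflation. This is an improvement that should be made, not a fault that invalidates the design.

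**What to change.** - **Sections 8.2.2.1 and 8.2.3:** prespecify the ORR with 95% CI in the All Patients as Treated population, as a sensitivity analysis reported beside the evaluable-subject ORR. Treated subjects without a week-12 response assessment count as non-responders, and death before re-staging is named explicitly.
- **Subjects who stop early without progression but are re-staged:** say how they are classified. They meet neither evaluable definition in 8.2.2.1, yet 8.2.2.1 calls only the un-scanned unevaluable, while 5.8 would replace them. In the sensitivity analysis, a week-12 assessment that exists should count as observed.
- **Reporting:** list the number of unevaluable subjects, the reasons, and whether each was lost before or after itacitinib started.
- **Section 8.1:** add that the 10% error and 90.6% power refer to evaluable subjects.
- **Unchanged:** the primary denominator and stage bounds, unless the design is re-derived. Altering them mid-trial in an open-label study would be a data-aware change, with the power loss shown in Step 5.
- **Separate minor point:** section 2.1 describes the re-staging scan as PET/CT, while section 7.1.2.6 and flow-chart note 7 do not accept PET/CT in place of post-infusion imaging. These passages need to be reconciled, since they bear on what counts as re-staging.

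The cost is protocol and SAP wording; no visits, scans or subjects are added. The downside is a second ORR that is usually slightly lower and includes subjects who never reached itacitinib.

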#### **8.2.2.2 Safety Analysis Populations**

The All Patients as Treated (APaT) population will be used for the analysis of safety data in this study. The APaT population consists of all enrolled subjects who received at least one dose of study treatment with either itacitinib or pembrolizumab. At least one laboratory or vital sign measurement obtained subsequent to at least one dose of trial treatment is required for inclusion in the analysis of each specific parameter. To assess change from baseline, a baseline measurement is also required.

### **8.2.3 Statistical Methods**

#### Primary Objectives

1. Based on evaluable subjects, the objective response rate and 95% confidence interval will be calculated.
2. Toxicities will be graded, categorized and tabled. Toxicity tables will be separately constructed for cycles with pembrolizumab alone (cycles 1-2 and cycle  $\geq 5$ ) or pembrolizumab and itacitinib (cycles 3-4).

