## 1.0 TRIAL SUMMARY

Title:	Phase II study of Pembrolizumab and Itacitinib (INCB039110) for First Line Treatment of Metastatic Non-Small Cell Lung Cancer Expressing PD-L1
Abbreviated Title	Pembrolizumab and itacitinib (INCB039110) for NSCLC
Protocol Numbers	UPCC#09517; IRB#828910; NCT03425006; IND#137721
Trial Phase	Phase II
Study Center(s)	University of Pennsylvania
Study Population	The first line treatment of patients with metastatic PD-L1 positive non-small cell lung cancer (NSCLC)
Methodology	This is a single center, single arm phase 2 study to establish the safety and efficacy of itacitinib (also known as INCB039110) administered in combination with pembrolizumab in patients with metastatic PD-L1 positive non-small cell lung cancer (NSCLC).
Study Drugs, Dose and Regimen	
Study Drug(s)
 

• Itacitinib: a JAK 1 selective small molecule inhibitor; an investigational agent that is study supplied

• Pembrolizumab: a highly selective humanized monoclonal antibody (mAb)

 
Dose and Route of Administration
 

• Itacitinib: 200mg PO (extended release formulation)

• Pembrolizumab: 200mg IV infusion over 30 minutes

 
Regimen
 

• Treatment = 3 week (Q3W) dosing cycles

• Itacitinib: Once daily for Cycle 3 and Cycle 4 (up to 6 weeks)

• Pembrolizumab: Q3 week cycles of treatment beginning at Day 1; if the PI considers it beneficial for the subject, a fifth cycle may be administered prior to EOS visit.

Number of trial subjects	Up to 48 evaluable subjects
Estimated duration of trial	Approximately 48 months

CONFIDENTIAL

This material is the property of the University of Pennsylvania. Do not disclose or use except as authorized in writing by the study sponsor.

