**Table 21: Trial Treatment**

Drug	Dose/Potency	Dose Frequency	Route of Administration	Regimen	Use
Pembrolizumab	200 mg	Q3W	IV infusion	Day 1 of each 3-week cycle; up to 4 study treatment cycles*	Per label- with the exception of the drug being administered with itacitinib
Itacitinib (INCB039110)	200 mg	Once Daily	Oral	Daily for cycles 3-4 (q3 weeks); up to 42 days of therapy	Investigational

The pembrolizumab dosing interval may be modified as per package insert.  
\*If the PI considers it beneficial for the subject, a fifth cycle may be administered prior to EOS visit.

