### 5.3.2 Timing of Dose Administration

Trial treatment should be administered on Day 1 of each cycle after all procedures/assessments have been completed as detailed on the Trial Flow Chart ([Section 6.0](#)). Trial treatment may be

CONFIDENTIAL

This material is the property of the University of Pennsylvania. Do not disclose or use except as authorized in writing by the study sponsor.

administered up to 3 days before or after the scheduled Day 1 of each cycle due to administrative reasons.

All trial treatments will be administered on an outpatient basis.

Pembrolizumab will be administered q3 weeks as a 30 minute IV infusion. Up to 4 cycles of pembrolizumab will be administered as part of this study. If the PI considers it beneficial for the subject, a fifth cycle may be administered prior to EOS visit. Pembrolizumab treatment cycle intervals may be increased due to toxicity as per package insert. Sites should make every effort to target infusion timing to be as close to 30 minutes as possible. However, given the variability of infusion pumps, a window of +/- 10 minutes is permitted.

Itacitinib will be administered daily starting at Cycle 3/Day 1 and continue for a total of 6 weeks (42 days). Itacitinib should be taken orally by the subject at the prescribed dose- 200 mg QD (2 x 100 mg tablets). If dose reductions are required due to toxicity, the prescribed dose may be reduced to 100 mg QD (1 x 100 mg tablet). Itacitinib should be taken with water, and may be taken without regard to food. If itacitinib doses are missed due to toxicity (per [Table 3](#)) or if vomiting occurs, these missed doses will not be made up.

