##### **7.1.7.3 End of Study Visit**

The End of Study Visit will occur at Week 16 (+/-10d). If the PI considers it beneficial for the subject, a fifth cycle may be administered prior to EOS visit. Subjects who remained on study treatment beyond Week 16 prior to the approval of Protocol Amendment V5, will be asked to undergo an End of Study Visit at their next clinic appointment prior to being withdrawn from the study.

Any SAEs experienced after this visit must be reported to the sponsor if the investigator suspects a causal relationship to the study treatment. Once an adverse event is detected, it should be followed until its resolution or until it is judged to be permanent.

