### ***8.2 Statistical Analysis Plan***

Based on evaluable subjects, the objective response rate and 95% confidence interval will be calculated. Duration of remission, progression-free survival and overall survival will be estimated by the method of Kaplan and Meier. Median values and 95% confidence intervals will be calculated. All observed toxicities will be graded and tabled. Toxicity tables will be separately constructed for cycles with pembrolizumab alone (cycles 1-2 and cycle  $\geq 5$ ) or pembrolizumab and itacitinib (cycles 3-4). Changes in immune pharmacodynamic biomarkers will be examined with scatter plots and summary statistics. Fold changes from baseline values will be estimated and summarized. **Sample Size:** The required sample size ranges from 11 to 48 evaluable subjects. In the event that 5% of subjects are not evaluable for objective response evaluation, the maximum sample size is 50 subjects. **Study Duration:** With an estimated accrual of 2 patients per month, it is anticipated that accrual will continue for approximately 24 months and subject follow-up will continue for up to year post Cycle 1/Day 1 (initiation of study treatment) for a total study duration of up to 36 months.

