### **Adverse Event Reporting Period**

Collection of adverse events will begin at the time of consent and continue through the End of Study Visit.

After the End of Study Visit, any SAE that the investigator becomes aware of must be reported to the sponsor if the investigator suspects the event may reasonably be related to the study treatment.

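### The pembrolizumab-alone toxicity table pools cycles before itacitinib with cycles after it, and the plan does not say where an event starting after cycle 4 is counted

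*Combined protocol and SAP*

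**What the plan says.** Section 8.2.1 names tolerability as one of two primary endpoints, alongside objective response rate. Its analysis is tabulation. Section 8.2 promises that "All observed toxicities will be graded and tabled". Sections 8.2 and 8.2.3 then give the same two-way split: "Toxicity tables will be separately constructed for cycles with pembrolizumab alone (cycles 1-2 and cycle" 5 onward) in one set, and cycles 3-4, with both drugs, in the other. No table shells are given.

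The regimen and calendar come from elsewhere:
- Section 1.0: "Treatment = 3 week (Q3W) dosing cycles".
- Section 5.3.2: "Itacitinib will be administered daily starting at Cycle 3/Day 1 and continue for a total of 6 weeks (42 days").
- Section 5.3, footnote to the trial treatment table: "If the PI considers it beneficial for the subject, a fifth cycle may be administered prior to EOS visit".
- Section 7.1.7.3: "The End of Study Visit will occur at Week 16 (+/-10d"). The same section provides for a further group: "Subjects who remained on study treatment beyond Week 16 prior to the approval of Protocol Amendment V5".
- Section 10.1: "Collection of adverse events will begin at the time of consent and continue through the End of Study Visit". The flow chart in 6.1 also marks an adverse event assessment at that visit.
- Section 7.1.7.2.1, by contrast, has adverse events followed through the End of Treatment Safety Follow-Up Visit at week 12.

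**The concern.** The split appears intended to show toxicity with and without itacitinib. The trial has one arm, so cycles 1-2 are the only planned time in which subjects have had pembrolizumab and no itacitinib. Section 4.1.2 says that the risks of the combination are not known. If time after itacitinib goes under the same label as cycles 1-2, the tables cannot show toxicity before, during and after itacitinib. An event that emerges after the combination is then read as belonging to pembrolizumab alone.

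The second problem is a missing rule. The strata are named by cycle number, while adverse event collection runs past the last planned cycle. Two programmers could place the same week-14 event differently, or leave it out of both split tables, and each could claim to have followed the plan.

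**Working it through.** **Timeline.** The plan gives no figure for this point, so the first step is to check that the schedule is consistent. Four cycles of 21 days make 84 days, or 12 weeks, which agrees with the 12 weeks in Section 2.1. Counting days from first dose, on the planned schedule with the full 42 days of itacitinib:
- cycles 1-2: days 0-42, no itacitinib yet
- cycles 3-4: days 42-84, both drugs
- optional cycle 5: days 84-105, after itacitinib
- End of Study: day 112, with a window of 102 to 122

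**Pooling.** Share of pembrolizumab-alone time that follows itacitinib = post-itacitinib days / (42 + post-itacitinib days).
- No fifth cycle: 0/42 = 0%.
- Fifth cycle of 21 days: 21/(42 + 21) = 21/63 = 33.3%.
- Fifth cycle cut short by the earliest visit (day 102): 18/(42 + 18) = 18/60 = 30.0%.
- Fifth cycle read as running to End of Study (day 112): 28/(42 + 28) = 28/70 = 40.0%.
- Subjects treated beyond week 16 before Amendment V5: a larger share, but the documents give neither their number nor their duration, so no figure can be set.

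**Events after cycle 4, no fifth cycle.** The result depends on a convention that the plan does not state.
- Cycle 4 ends on day 84 and later events belong to no named cycle: unassigned share = (112 - 84)/112 = 28/112 = 25.0%. Earliest visit: 18/102 = 17.6%. Latest visit: 38/122 = 31.1%.
- Events belong to the last cycle started: they fall in cycle 4, hence in the combination table, and the unassigned share is 0%.

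**Events after a fifth cycle.** 112 - 105 = 7 days remain (0 with the earliest visit, 122 - 105 = 17 with the latest). None remain if cycle 5 is read as running to End of Study.

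All of these are shares of planned time, not of events. The documents do not say how many subjects receive a fifth cycle.

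**Length of follow-up.** Sections 10.1 and 6.1 carry adverse events to week 16, while 7.1.7.2.1 names the week-12 visit. If collection stopped at week 12, the 28 days after cycle 4 would largely disappear. The passages must be reconciled.

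**The case against.** The strongest reply has four parts.

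1. The label is literally correct: pembrolizumab is the only drug given from cycle 5 onward, and classifying by drug administered is a recognisable choice. No section promises a formal comparison between the two sets of tables. This stands as far as it goes. But the two kinds of time differ in prior exposure, and showing them separately loses nothing.

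2. The pooling touches few subjects under the current regimen: those given an optional fifth cycle, and those treated past week 16 before Amendment V5. This also stands. The reference to cycle 5 onward may be retained from before that amendment, but it still governs both groups.

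3. A reader might infer that weeks 12-16 have no stratum at all, so that a quarter of follow-up drops out of the split tables. The documents do not support this as fact. The strata are cycle numbers, and assigning events to the last cycle started is an ordinary convention that would close the gap. What stands is that neither convention is written down.

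4. The tables are descriptive and all toxicities are tabled anyway. True, and this limits the consequence. Yet tabulation is the stated analysis of this primary endpoint, and an overall table cannot separate before, during and after.

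**Conclusion.** The point holds in two parts. First, as written, the pembrolizumab-alone table mixes itacitinib-naive and post-itacitinib time for any subject with a cycle beyond the fourth. With a fifth cycle, about one third of that subject's pembrolizumab-alone time comes after itacitinib. Second, the rule for placing events after cycle 4 is unstated when no fifth cycle is given, which leaves 0% to 25% of planned time (31% with the latest visit) unassigned. These figures assume 21-day cycles without delay, 42 full days of itacitinib, and adverse event collection to week 16.

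The consequence is limited. The number of events affected is unknown and may be zero, and the direction of any misclassification is not established. Sample size and the response-rate decision do not change. A reader might infer that the safety conclusion is biased, or that toxicity monitoring is compromised. The documents support neither. The stopping rule in Section 5.9 does not refer to the split. It sends the definition of unacceptable toxicity to Section 8.1, and the text available for this review shows none there, so its independence from the split cannot be fully confirmed.

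This is worth correcting as a cheap improvement to how a primary endpoint is reported.

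**What to change.** In Sections 8.2 and 8.2.3, stop pooling cycles 1-2 with cycle 5 onward. Assign each event by onset date to one of three periods, shown separately:
1. from the first pembrolizumab dose to before the first itacitinib dose (to End of Study for a subject who never takes itacitinib);
2. from the first itacitinib dose through a stated analysis window after the last one;
3. after that window through End of Study, whether or not a fifth cycle is given.

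The sponsor must choose and state the window, since the documents give none. Without a window, an event starting the day after the last dose would leave the combination period. Define the periods by dose dates, not cycle numbers, because Table 3, note 2, lets a subject stop itacitinib and stay on pembrolizumab. Use as denominator the subjects under observation in each period, and report the observation time per period, because the periods differ in length. Keep one overall table in the All Patients as Treated population. Reconcile Section 7.1.7.2.1 with 10.1 and 6.1 on how long adverse events are followed.

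The cost is wording and table shells. Section 10.2 already asks for start and end dates of each event, so no new data, visits or subjects are needed. The downside is that onset periods do not settle causality: some toxicity due to pembrolizumab, including late effects of cycles 1-2, will fall in the second or third period.
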